7.6.1 Safety parameters

Safety endpoints and tolerability will be analysed as described in [Section 7.8](#) of this TSAP.

7.7 EXTENT OF EXPOSURE

Since only a single dose is administered per subject a listing will be sufficient to give account of the extent of exposure.

7.8 SAFETY ANALYSIS

All safety analyses will be performed on the TS, except for the exposure-response analysis which will be based on the ECGPCS.

7.8.1 Adverse Events

AEs will be coded with the most recent version of MedDRA.

The analyses of AEs will be descriptive in nature. All analyses of AEs will be based on the number of subjects with AEs and not on the number of AEs.

For further details on summarization of AE data, please refer to "Analysis and Presentation of Adverse Event Data from Clinical Trials" (7) and "Handling of missing and incomplete AE dates" (3).

The analysis of AEs will be based on the concept of treatment emergent AEs. That means that all AEs will be assigned to screening or on-treatment phase as defined in [Section 6.1](#). AEs will be analysed based on actual treatments, as defined in [Table 6.1: 1](#).

An overall summary of AEs will be presented. This overall summary will comprise summary statistics for the class of AESIs.

CTP: Hepatic injury is considered an AESI in this trial. A hepatic injury is defined by the following alterations of hepatic laboratory parameters:

- *An elevation of AST (aspartate transaminase) and/or ALT (alanine transaminase) ≥ 3 fold ULN combined with an elevation of total bilirubin ≥ 2 fold ULN measured in the same blood sample, or*
- *Aminotransferase (ALT, and/or AST) elevations ≥ 10 fold ULN*

The investigator had to classify on the eCRF whether an observed AE was an AESI or not.

According to ICH E3 ([8](#)), in addition to Deaths and Serious Adverse Events, 'other significant' AEs need to be listed in the clinical trial report. These will be any non-serious adverse event that led to an action taken with study drug (e.g. discontinuation or dose reduced or interrupted).

The frequency of subjects with AEs will be summarised by treatment, primary SOC and preferred term. AEs which were considered by the investigator to be drug related will be summarised separately. Separate tables will also be provided for subjects with SAEs and subjects with AESIs. AEs will also be summarized by maximum intensity.

The SOCs and preferred terms within SOCs will be sorted by descending frequency over all treatment groups.

For disclosure of AE data on ClinicalTrials.gov, the frequency of subjects with non-serious AEs occurring with an incidence of greater than 5 % (in preferred terms) will be summarised by treatment, primary SOC and preferred term. The frequency of subjects with SAEs will also be summarised.

For disclosure of AE data in the EudraCT register, the frequency of AEs, the frequency of non-serious AEs with an incidence of greater than 5 % (in preferred terms) and the frequency of SAEs will be summarized.

For support of lay summaries, the frequency of subjects with drug-related SAEs will be summarized by treatment, primary SOC and preferred term.

7.8.2 Laboratory data

The analyses of laboratory data will be descriptive in nature and will be based on BI standards "Display and Analysis of Laboratory Data" ([9](#)).

Analyses will be based on normalised values, which means transforming to a standard unit and a standard reference range. The original values will be analysed if the transformation into standard unit is not possible for a parameter.

Descriptive statistics of laboratory values over time and for the difference from baseline (see [Section 6.7](#)) will be provided. Frequency tables of changes between baseline and last value on treatment with respect to the reference range will be presented.

Unscheduled measurements of laboratory data will be assumed to be repeat measurements of the most recent scheduled measurement (e.g. for follow-up or confirmation of a particular value). Therefore, unscheduled measurements will be assigned to the planned time point of the previous scheduled measurement. Descriptive statistics will be calculated by planned time point based on the worst value of the subject at that planned time point (or assigned to that planned time point).

Clinically significant abnormal laboratory values are only those identified either in the Investigator's comments or at the Report Planning Meeting at the latest. It is the Investigator's responsibility to decide whether a lab value is clinically significant abnormal or not.

Laboratory data will be compared to their reference ranges. Values outside the reference range as well as possibly clinically significant values will be highlighted in the listings. Possibly clinically significant laboratory values will be listed separately.

Clinically relevant findings in laboratory data will be reported as baseline conditions (prior to start of infusion) or as AEs (after start of infusion) if judged clinically relevant by the investigator, and will be analyzed as such.

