## FLOW CHART

Visit	Day	Planned time (relative to drug administration) [h:min]	Approximate clock time of actual day [h:min]	Event and comment	Safety laboratory	PK blood 	Body temperature	12-lead ECG	Continuous ECG monitoring	Vital signs (BP, PR)	Questioning for AEs and concomitant therapy 
1	-21 to -3			Screening (SCR) 	A		x	x		x	
2	-2	-48:00	08:00	Ambulatory visit 	B 		x			x	
	-1	-12:00	20:00	Admission to trial site	x 		x			x	
	1	-3:00	06:00	Allocation to treatment 	B 	x 	x 	x 	▲	x 	x 
		0:00	08:00	Drug administration start of infusion			x 			x	x 
		0:30	08:30	end of infusion		x	x 			x	x 
		1:00	09:00			x	x 			x	x
		1:30	09:30				x 			x	x
		2:00	10:00	light breakfast 		x	x 			x	x 
		3:00	11:00			x	x 			x	x
		4:00	12:00	lunch 	x 	x	x 	▼		x	x
		6:00	14:00			x	x 			x	x
		8:00	16:00	Snack (voluntary) 		x	x 			x	x
		10:00	18:00	Dinner 		x					
		12:00	20:00			x	x 			x	x
	2	24:00	08:00	Breakfast 	B 	x	x 			x	x
		34:00	18:00	Dinner 		x	x 			x	x
	3	48:00	08:00	Breakfast  discharge from trial site (confirmation of fitness  )		x	x 			x	x
	4	72:00	08:00	Ambulatory visit	B	x	x			x	x
	7	144:00	08:00	Ambulatory visit	B	x	x			x	
	14	312:00	08:00	Ambulatory visit		x	x			x	
	21	480:00	08:00	Ambulatory visit	B	x	x			x	
	28	648:00	08:00	Ambulatory visit		x	x			x	
	56	1320:00	08:00	Ambulatory visit	B	x 	x			x	
	84	1992:00	08:00	Ambulatory visit		x 	x			x	
3	84-87			End of trial (EoTrial) examination 	B		x	x		x	x

1. Subject must be informed and written informed consent obtained prior to starting any screening procedures. Screening procedures include physical examination, check of vital signs and body temperature, ECG, safety laboratory (including drug screening), demographics (including determination of body height, weight, smoking status, alcohol history, relevant medical history, concomitant therapy, and review of inclusion/exclusion criteria).

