2. The time is approximate; procedures are to be performed and completed within the 3 h prior to drug administration. Allocation to treatment may be performed at any time following enrolment but must be completed prior to (first) drug administration.
3. If several actions are indicated at the same time, the intake of meals will be the last action.
4. At the end of trial visit the EoTrial examination includes physical examination, body weight, vital signs, ECG, safety laboratory, recording of AEs, and concomitant therapies. EOT to be performed not before last PK sampling.
5. Only urine drug screening and alcohol breath test will be done at this time.
6. AEs and concomitant therapies will be recorded throughout the trial, but will be specifically asked for at the times indicated in the [Flow Chart](#) above.

Proprietary confidential information © 2021 Boehringer Ingelheim International GmbH or one or more of its affiliated companies

7. Safety laboratory to be taken and to be medically evaluated within 3 days prior to administration of study drug; this safety laboratory assessment can be omitted if the screening examination is performed on Days -5 to Day -3.
8. The ECG recording has to be performed in triplicate ECGs at this time
9. Sampling times and periods may be adapted based on information obtained during the trial (e.g., due to preliminary PK data) including addition of samples and visits as long as the total blood volume removed does not exceed 500 mL per subject
10. At baseline (i.e. Day 1, prior to drug administration) 3 triplicate ECGs are recorded within approximately one hour. The recordings should be separated by at least 15 minutes.
11. In case blood levels still exceed LOQ, additional PK [REDACTED] samples may be collected beyond Day 28.

[figure not shown]
14. SARS-CoV-2 PCR test will be performed.
15. Confirmation of fitness includes physical examination.
16. Letters A and B describe different sets of safety laboratory examinations (see Section [5.2.3](#)).
17. Local tolerability inclusive.

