### **1.2.6 Residual Effect Period**

The residual effect period (REP) of BI 765080, when measurable drug levels or PD effects are still likely to be present, is not known for this first-in-human trial. Conservatively, a minimum observation period of approximately 4-fold the estimated  $t_{1/2}$  has been selected. Therefore, the individual subject's end of trial is on Day 84-87 following dosing with investigational drug at the earliest (see [Flow Chart](#)).

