### **7.3.4 Safety analyses**

Safety will be assessed as defined by the endpoints listed in Sections [2.1.2](#) and [2.2.2](#) based on the treated set (TS). Safety analyses will be descriptive in nature and will be based on BI standards.

For all analyses the treatment actually administered (= treatment at onset) to the subject will be used (any deviations from the randomised treatment will be discussed in the minutes of the Report Planning Meeting).

Treatments will be compared in a descriptive way. The placebo group in the safety evaluation will consist of all subjects treated with placebo, regardless of the dose group in which they were treated. The test treatment groups will be compared to the placebo group in a descriptive way. Tabulations of frequencies/proportions will be used for the evaluation of categorical (qualitative) data, and tabulations of descriptive statistics will be used to analyse continuous (quantitative) data.

Measurements (such as ECGs, vital signs, or laboratory parameters) or AEs will be assigned to treatments (see Section [4.1](#)) based on the actual treatment at the planned time of the measurement or on the recorded time of AE onset (concept of treatment-emergent AEs).

Therefore, measurements planned or AEs recorded prior to the intake of trial medication will be assigned to the screening period; those between the trial medication intake and the end of

Proprietary confidential information © 2021 Boehringer Ingelheim International GmbH or one or more of its affiliated companies

trial examination (including the anticipated REP) will be assigned to the treatment period. These assignments including the corresponding time intervals will be defined in detail in the TSAP. Note that AEs occurring after the last per protocol contact but entered before database lock will be reported to Pharmacovigilance only and will not be captured in the trial database.

Adverse events will be coded using the Medical Dictionary for Regulatory Activities (MedDRA). Frequency, severity, and causal relationship of AEs will be tabulated by treatment, system organ class and preferred term. SAEs, AESIs (see Section [5.2.6.1](#)) and other significant AEs (according to ICH E3) will be listed separately.

Previous and concomitant therapies will be presented per treatment group without consideration of time intervals and treatment periods.

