6. GENERAL ANALYSIS DEFINITIONS

6.1 TREATMENTS

For basic study information on treatments to be administered, assignment of treatment groups, and selection of doses, cf. Section 4 of the CTP.

Subjects will receive a 30 minutes intravenous infusion containing

- powder for solution of either a single dose of 1, 10, 25, 50, 100 or 200 mg of BI 765080 (test treatments)
or
- a matching placebo (reference treatment)

All placebo subjects will be analysed in one pooled placebo group (i.e. no distinction between dose groups will be made for placebo subjects).

For statistical analysis of AEs, the following analysis phases are defined for each subject.

Table 6.1: 1 Analysis phases for statistical analysis of AEs, and actual treatment for analysis of laboratory data, vital signs, ECG and local tolerability

Study analysis phase		Label	Start	End
Screening ¹		Screening	Date of informed consent	Date/time of start of infusion
On treatment	Placebo, 1 mg BI, 10 mg BI, 25 mg BI, 50 mg BI, 100 mg BI or 200 mg BI respectively		Date/time of start of infusion	12:00 a.m. on day after last contact date

¹ See [Section 6.7](#) for definition of baseline, which will be used in the statistical analyses of safety laboratory data, ECG and vital signs.

AE summary tables will present results for the on-treatment phase only. All AEs will be listed.

In AE tables in CTR Section 15.3 (but not in Appendix 16.1.13.1.8.1 and Appendix 16.1.13.1.8.2 AE tables), the following total will be provided in addition:

- "**Total BI**", defined as the total over all on-treatment phases involving BI

- "**Total on-trt**", defined as the total over all on-treatment phases, including placebo

Safety laboratory data, ECG, vital signs, PK, immunogenicity and exploratory biomarker parameters will be analysed based on treatment groups (Placebo, 1 mg BI, 10 mg BI, 25 mg BI, 50 mg BI, 100 mg BI or 200 mg BI) with clear differentiation between baseline (cf. [Section 6.7](#)) and on-treatment measurements. Measurements will be considered on-treatment, if they were taken within the on-treatment phases as defined in [Table 6.1: 1](#).

More details on the technical implementation of these analyses are provided in the ADS Plan of this TSAP.

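### Laboratory shift tables use only the last on-treatment value, which for completers is the Day 84-87 sample, so abnormalities that resolve earlier are not counted in them

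*SAP*

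**What the plan says.** SAP 7.8.2 defines the shift tables in one sentence: "Frequency tables of changes between baseline and last value on treatment with respect to the reference range will be presented".

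The on-treatment window comes from SAP 6.1: "Measurements will be considered on-treatment, if they were taken within the on-treatment phases as defined in" Table 6.1: 1. That table starts the phase at the start of infusion and ends it at "12:00 a.m. on day after last contact date". There is no separate follow-up phase. Protocol 7.3.4 agrees: data from dosing to the end of "trial examination (including the anticipated REP) will be assigned to the treatment period".

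The flow chart's last visit is the "End of trial (EoTrial) examination", Visit 3 on Days 84-87, with a set B laboratory panel. Footnote 4 confirms this: "At the end of trial visit the EoTrial examination includes physical examination, body weight, vital signs, ECG, safety laboratory". Protocol 1.2.6 sets the timing at about four times the estimated half-life and adds that "the individual subject's end of trial is on Day 84-87 following dosing with investigational drug at the earliest".

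The other planned laboratory displays in SAP 7.8.2 are descriptive statistics by planned time point, highlighting of out-of-range values in listings, and a separate listing of possibly clinically significant values. Findings that the investigator judges clinically relevant are reported as AEs.

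**The concern.** A shift to the last value suits repeated dosing, where the last sample is still taken under drug. Here each subject receives one infusion and is then followed for about twelve weeks. The last sample mainly answers whether values have returned to the reference range, not whether they left it.

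The SAP's own ECG section takes the other approach. In SAP 5.3.1 the QTcF and QT categories use the maximum on treatment, with new onset assessed over all on-treatment time points, and notable findings count at any time on treatment. No reason is given for treating laboratory data differently, although the trial's only AESI, hepatic injury, is defined by laboratory thresholds.

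What is at stake is how a first-in-human safety table is read. A row of zeros could be taken as no laboratory effect at that dose when several subjects had been out of range and recovered.

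**Working it through.** The plan gives no figure to reproduce here. The check is which samples the shift table can use.

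**Scheduled post-dose set B panels (protocol flow chart; day = hours/24 + 1)**

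| Planned time | Study day | Used in shift table for a completer? |
|---|---|---|
| 24 h | 2 | No |
| 72 h | 4 | No |
| 144 h | 7 | No |
| 480 h | 21 | No |
| 1320 h | 56 | No |
| End of trial, from 1992 h | 84-87 | Yes |

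All six lie inside the on-treatment window, so all are eligible, but the last-value rule selects only the sixth. The flow chart also marks a laboratory entry at 4 h. It is not counted because its footnote is not legible in the public document. The gap between the Day 56 panel and the earliest end-of-trial sample is (1992 − 1320)/24 = 28 days.

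**Time since dose.** Day 84 is 1992/24 = 83 days after infusion and Day 87 is 86 days. If this is four half-lives, the half-life is 83/4 = 20.75 to 86/4 = 21.5 days, and 0.5^4 = 6.25% of drug remains. This assumes single-exponential decline and takes the protocol's approximate factor of four at face value. The human PK prediction itself is redacted.

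**Effect on the count.** If k of 6 active subjects are out of range at some panel and back in range by end of trial, the planned table shows 0/6 and a highest/lowest-value table shows k/6. For k = 3 that is 0/6 against 3/6.

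**How slow recovery must be for the last value to register it (illustration, assumed figures).** Take a value of 10 × ULN on Day 4 that falls with half-life r days. On Day 84 it is 10 × 0.5^(80/r):

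- r = 7: 0.004 × ULN
- r = 14: 0.19 × ULN
- r = 21: 0.71 × ULN
- r = 28: 1.38 × ULN

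Only the slowest of these is still above range.

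**Price of using the extreme value.** Assume each sample has an independent 2.5% chance of being above range by chance, and the same below. One sample gives 2.5% per table. The highest (or lowest) of six gives 1 − 0.975^6 = 0.141, about 14%. Among 6 active subjects the expected background count rises from 6 × 0.025 = 0.15 to 6 × 0.141 = 0.85. Among the 12 planned placebo subjects it rises from 0.3 to 1.7. Unscheduled retests raise it further for the subjects retested.

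**The case against.** The strongest reply is that the neighbouring displays already show a transient change. SAP 7 requires minimum, median and maximum as well as mean and SD. SAP 7.8.2 builds the by-visit tables from each subject's worst value at each planned time point. With 6 subjects per dose, one raised ALT sets the Day 7 maximum, and three raised values move the median. Listings are sorted by treatment, so flagged subjects can be counted by hand. Important findings are counted by group as AEs, and hepatic injury as an AESI. The trial tests no hypothesis, and dose escalation uses the safety review data, not this table.

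Most of that stands, and it limits the point to one display. Three things remain:

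- By-visit extremes do not say how many subjects left the range.
- The worst-value rule works within one planned time point and governs the descriptive statistics, so it does not change the shift table.
- AE counts include laboratory changes only if the investigator judges them clinically relevant, and protocol 4.1.5.1 says the investigator knows the treatment.

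The sponsor's laboratory display standard and the ADS Plan, both cited in the SAP, are not available. Either could add a further frequency table.

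A reader might infer that a transient laboratory effect cannot appear in the shift tables at all, or that the trial would miss it. The documents support neither. An abnormality still present at Day 84-87 would be counted. A subject who discontinues early has the end-of-trial examination at that time if possible (protocol 3.3.4), so the last value is an earlier one.

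**Conclusion.** The point holds as a limited weakness in one display. For completers, the shift table uses 1 of 6 scheduled post-dose set B panels, taken 83-86 days after a single dose, and does not count abnormalities that have resolved by then. The SAP text states no other by-group count of subjects leaving the reference range that is independent of the unblinded investigator's view of clinical relevance.

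This does not bias a planned estimate, affect the primary or secondary endpoints, or lose data. It rests on reading the last on-treatment value through Table 6.1: 1, on subjects completing with an end-of-trial sample, and on the unseen sponsor standard not defining the table differently. It is a minor improvement, worth making because it is cheap.

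**What to change.** In SAP 7.8.2, present shifts relative to the reference range from baseline to the highest on-treatment value and, in a separate table, to the lowest. Draw on all post-dose samples, scheduled and unscheduled, and show each dose group and pooled placebo under the same rule. This brings laboratory data into line with the maximum-on-treatment rule already used for ECG. Keep the last-value table and label it as a display of reversibility. If the sponsor's laboratory standard already produces such tables, a sentence in the SAP saying so is enough.

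The cost is a short SAP text change and further runs of an existing table program, with no new data. The drawback is the higher background count shown above. A footnote should tell readers to judge each dose against pooled placebo, and note that retested subjects have more chances to be out of range.

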6.7 BASELINE, TIME WINDOWS AND CALCULATED VISITS

In all analyses (except for analyses of ECG variables), baseline is defined as the last available value prior to start of infusion.

A centralised evaluation of 12-lead ECG recordings is performed at the time points specified in [Table 6.7: 1](#)

Table 6.7: 1 Time schedule of 12-lead ECG recordings with centralised evaluation

Visit	Day	Planned time [hh:mm] - relative to start of infusion	Study phase
2		-3:00	Baseline
		00:30	On-treatment
		01:00	
		01:30 ¹	
		02:00	
		03:00	
		04:00	
		06:00	
		08:00	
	1	12:00	
2		24:00	
		34:00	
3		48:00	

¹ According to CTP flow chart, there is no time-matched PK sample for the ECG measurement at planned time 1:30. This ECG measurement will not be used in the exposure-response model, which will be applied to time matched pairs of ECG measurements and PK samples.

Three triplicate ECGs will be recorded as the baseline before drug administration, but only the first ECG of each of the 3 baseline triplicate will be transferred to the database. At all other time points, 1 triplicate ECG will be recorded, but only the first single ECG of the triplicate will be transferred to the database. The baseline value of an ECG variable is defined as the mean of the ECG variable values prior to drug administration.

Additional (unscheduled) ECGs may be recorded for safety reasons. These ECGs are assigned to the prior scheduled time point in the sponsor's database. Unscheduled ECGs (for safety reasons) will be transferred to the central ECG lab but will not be included into the statistical analysis of interval lengths.

For the exposure response analyses, pairs of ECG variables and corresponding serum concentrations will be built using the same planned time points, e.g., the HR change from baseline and the serum concentration measured at planned time 0:30 will build one pair. Whether a time deviation between PK blood sampling time and corresponding ECG recording is too big for a reliable assessment and the pair has to be excluded from the analysis will be decided no later than at the RPM.

Time windows are defined in Section 6.1 of the CTP. Adherence to time windows will be checked at the Report Planning Meeting.

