7.8.3 Vital signs

The analyses of vital signs (blood pressure and pulse rate) will be descriptive in nature. Descriptive statistics of vital signs over time and for the difference from baseline (see [Section 6.7](#)) will be provided.

Unscheduled measurements of vital signs will be assigned to planned time points in the same way as described above for laboratory data. However, for vital signs, descriptive statistics will be calculated by planned time point based on the last value of the subject at that planned time point (or assigned to that planned time point).

Clinically relevant findings in vital signs data will be reported as baseline conditions (prior to start of infusion) or as AEs (after start of infusion) if judged clinically relevant by the investigator, and will be analyzed as such.

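### SAP 7.8.2 moves unscheduled laboratory values back to the previous scheduled time point with no exception at the start of infusion, so an early post-dose value can land in the pre-dose row, against SAP 6.1 and 6.7

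*SAP*

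**What the plan says.** SAP 7.8.2 treats any unscheduled laboratory value as a repeat of the most recent scheduled one and gives it that sample's slot: "Therefore, unscheduled measurements will be assigned to the planned time point of the previous scheduled measurement". It continues: "Descriptive statistics will be calculated by planned time point based on the worst value of the subject at that planned time point", which includes values assigned to that point. SAP 7.8.3 carries the assignment rule over to vital signs ("Unscheduled measurements of vital signs will be assigned to planned time points in the same way as described above for laboratory data") but summarises the last value instead of the worst.

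Two other SAP sections use the actual time. SAP 6.1 asks for baseline and on-treatment data to be kept clearly apart and says: "Measurements will be considered on-treatment, if they were taken within the on-treatment phases as defined in" Table 6.1: 1, where the on-treatment phase opens at the start of infusion. SAP 6.7 says, for everything except ECG variables, that "baseline is defined as the last available value prior to start of infusion".

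Protocol 7.3.4 assigns measurements "based on the actual treatment at the planned time of the measurement", and leaves the detailed definition of these assignments and intervals to the TSAP.

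**The concern.** The repeat assumption is reasonable when nothing has happened between the scheduled sample and the extra one. It fails when a dose has been given in between, because the later value then describes a different state of the subject.

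The protocol foresees such samples. Section 4.1.4 provides for infusion reactions, section 5.2.3 for event-driven blood draws after a potential systemic allergic reaction, and section 5.2.6.1.4 for unscheduled blood tests if hepatic symptoms appear. Sections 1.4.2 and 3.1 place the time of peak concentration and of highest risk at about the end of infusion. A value drawn then, probably because something was noticed, would sit in the row that a reader takes as the untreated state. The worst-value rule makes it more likely that the abnormal post-dose result, and not the true pre-dose one, fills that cell.

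**Working it through.** The plan gives no figure to reproduce: the point concerns a data-handling rule, and protocol 7.2 plans no hypothesis test. The check applies the rule to the schedule and then sizes one occurrence.

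**Step 1: the schedule.** Laboratory entries in the protocol Flow Chart around dosing:

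- Day 1, -3:00: set B ("Allocation to treatment 2 B 13")
- Day 1, 0:00: infusion starts, no laboratory entry
- Day 1, 4:00: an entry marked x, not lettered B
- Day 2, 24:00: set B ("Breakfast 3 B 13")

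Footnote 13 belongs to all three laboratory entries, but its text is not visible in the copy reviewed. The content of the 4:00 sample is therefore unknown here.

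**Step 2: the rule applied.** Take an unscheduled sample at 1:00. The previous scheduled laboratory measurement is the one at -3:00, so SAP 7.8.2 gives it the -3:00 slot. The same holds for any unscheduled sample from the start of infusion until just before 4:00. For a parameter not measured at 4:00, it may hold until just before 24:00.

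**Step 3: the same sample under the other rules.**

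- SAP 6.1: taken after the start of infusion, so on-treatment.
- SAP 6.7: not taken before the infusion, so it cannot be baseline.
- SAP 7.8.2: tabulated at a pre-dose planned time.

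The first two agree with each other and disagree with the third.

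**Step 4: size of one occurrence.** Shift in the row mean = (post-dose value - true pre-dose value) / n. Protocol 3.1 gives n = 6 active subjects per dose. The pooled placebo group has 6 dose groups x 2 = 12. The documents give no laboratory values, so these are assumed:

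- pre-dose 20 U/L, 200 U/L at 2 h: excess 200 - 20 = 180 U/L
- active group: 180 / 6 = 30 U/L
- pooled placebo: 180 / 12 = 15 U/L
- smaller assumed excess of 20 U/L, active group: 20 / 6 = 3.3 U/L

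For a parameter whose worst value is a low one, the shift is downward.

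**Step 5: what stays unchanged.** Under SAP 6.7 this subject's baseline remains 20 U/L, so changes from baseline at 4:00 and later are the same as without the extra sample. If the change-from-baseline table carries the -3:00 row, that row would show a mean change of 30 U/L before any drug was given, which makes the conflict visible. The shift table compares baseline with the last on-treatment value, so an early transient abnormality would not appear there under either rule.

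**Step 6: vital signs.** These are scheduled at -3:00, 0:00 and 0:30. A reading at 0:10 goes back to 0:00 and, as the last value, displaces the start-of-infusion reading. It does not enter the -3:00 row.

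**The case against.** The strongest reply is that SAP 6.1 already settles the matter. It names safety laboratory data and vital signs, requires baseline and on-treatment data to be kept apart, and classes measurements by the time taken. A careful programmer would let that prevail. SAP 6.1 also refers to an ADS Plan for implementation, and SAP 7.8.2 to a sponsor standard for laboratory displays. Neither is available here, and either may contain the missing condition. This lowers the chance of a wrong table but does not remove the gap: SAP 7.8.2 is the section that says which row a value goes in, it states no exception, and nothing says that SAP 6.1 overrides it. The SAP does draw this line for ECGs, where 7.8.4 leaves out pre-dose recordings made after the infusion began, as well as unscheduled ones.

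A reader might infer three stronger things that the documents do not support:

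- **That the early signal is lost.** All individual values are listed, out-of-range values are highlighted, possibly clinically significant ones are listed separately, and a finding after the start of infusion that the investigator judges clinically relevant becomes an adverse event. Scheduled values at 4:00 and later keep their own rows.
- **That protocol 7.3.4 makes the value a screening value and must be amended.** Its planned-time wording points that way, but an unscheduled sample has no planned time of its own, and the section hands the detail to the TSAP.
- **That vital signs taken during infusion become pre-dose values.** The 0:00 row is the start of infusion, not clearly a pre-dose slot.

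**Conclusion.** The point holds as a conflict inside the SAP. Taken literally, 7.8.2 places an unscheduled laboratory sample drawn after the start of infusion, and before the next scheduled one, in the Day 1 pre-dose row, where it replaces the true value if it is worse. SAP 6.1 and 6.7 treat the same sample as on-treatment and not baseline.

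The consequence is limited to the by-time-point descriptive tables. It would be wrong to conclude that the value becomes baseline or that the count of subjects with drug-related adverse events changes.

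The size is one sixth of the excess per affected active subject, or one twelfth in pooled placebo. The U/L figures rest on assumed values. The effect arises only if an unscheduled sample is drawn in that window and is worse than the pre-dose value. The window is 4 h; its extension to 24 h depends on the unseen footnote. It is worth correcting because the affected hours are those of highest exposure in a first-in-human trial and the correction is small.

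**What to change.** Add to SAP 7.8.2, and apply by reference in 7.8.3:

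*A measurement taken after the start of infusion is never assigned to a pre-dose planned time point. The phase rule in Section 6.1 takes precedence over assignment to the previous scheduled time point. Such values are summarised in a separate unscheduled on-treatment row, for example as the worst value between the start of infusion and the next scheduled sample.*

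SAP 7.8.3 should also say on which side of dosing the 0:00 vital-signs row falls, and which value its unscheduled row shows.

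Moving the value forward to the next scheduled time would not be a good alternative. A 1 h laboratory value placed at 4:00 could displace the true 4:00 value under the worst-value rule. A 0:10 vital-signs reading placed at 0:30 would be superseded by the scheduled 0:30 reading under the last-value rule and vanish from the summary.

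The cost is a short SAP addition, one programming condition and one extra table row when such values exist. It needs no new data, and no protocol amendment, because protocol 7.3.4 leaves the detail to the TSAP.
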